2.4 Combination Restorative Therapy for Erectile Dysfunction

The development of ED therapeutics that focus on neurovascular regeneration and repair strategies are of great importance. A large body of *pre-clinical* work has demonstrated the effect of SWT alone (monotherapy) on angiogenesis and progenitor / stem cell recruitment for ED [2, 3, 8-11]. PRP monotherapy importantly is also supported by well-defined mechanistic insights obtained from rigorously conducted animal studies [12-19]. All the previous studies in humans have evaluated either IIEF scores and / or penile Doppler ultrasound hemodynamic parameters, but there has not been evaluation of the treatment as a combination. The proposed mechanisms of both interventions would

suggest that the combination therapy would act in a synergistic manner, with superiority over monotherapy. Success of our proposed work could fundamentally change the standard of care for ED and substantially improve the quality of life for tens of millions of men.

3. Study Objectives

3.1 Primary Objective:

To investigate and compare the safety of PRP and SWT vs placebo/sham treatment in men with mild-moderate ED.

3.2 Secondary Objective:

To study the treatment efficacy of PRP and SWT treatment vs placebo/sham treatment in men with mild-moderate ED.

4. Study Endpoints

4.1 Primary Endpoint (safety):

- Incidence of treatment emergent serious adverse events (TE-SAEs) in all patients during the study period. Adverse events will be recorded at every visit. The following contains a list of the anticipated adverse events:
 - Pain
 - Bruising
 - Swelling
 - Edema
 - Allergy
 - Penile Fracture
 - New Penile Curvature

4.2 Secondary Endpoints (efficacy):

- Change in IIEF-EF score from baseline to 3 and 6 months post-therapy compared to control group.
- Percentage of subjects that achieve minimal clinically important difference (MCID) in IIEF-EF from baseline to 3 and 6 months post-therapy compared to control group,
- Percentage of subjects who either decrease or discontinue use of PDE5i after three months post-therapy compared to control group.

4.3 Exploratory Endpoints:

- Differences in Doppler ultrasound parameters (PSV and EDV) from baseline to 6 months post-therapy compared to control group.
- Treatment satisfaction as assessed by EDITS questionnaire in all subjects.
- Changes in IPSS questionnaire between treatment and control group.
- Perceptions of therapeutic allocation between treatment and control group.

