7.4 Withdrawal Criteria

All subjects who either screen fails, is withdrawn from the study, or has completed all visits should be de-enrolled from the research database within 2 business days, in accordance with university policies (or respective institutional policy).

Subjects may be withdrawn from the study for any of the following reasons:

- a) A subject does not meet the eligibility criteria (the subject will be considered a screen failure).
- b) A subject withdraws consent.
- c) If a new treatment for erectile dysfunction is made available during the study duration, the investigator will inform the patient at a follow-up visit, and be offered withdrawal to utilize new treatment.
- d) A subject expires during protocol participation from causes other than the study treatment (not due to adverse events).
- e) At the discretion of the principal investigator for issues of non-compliance, or other behavioral factors.

8. Procedures Involved

60 men with Erectile Dysfunction (ED) of organic origin, that meet all of the inclusion and none of the exclusion criteria, will be randomized to receive either PRP+SWT, or placebo/sham in a 1:1 double-blinded fashion.

- a) Group A (30 subjects): Autologous PRP injection + SWT therapy. All subjects in this group will receive 2 sessions of autologous PRP penile injection with 30 ± 7 day treatment interval. 5mL of PRP will be injected at each session. Additionally, patients will receive a total of 3600 shocks over a five-week period, starting at initial PRP injection.
- b) Group B (30 subjects): Placebo (Normal Saline) + SHAM. All subjects in this group will receive 2 sessions of normal saline penile injection with 30 ± 7 day treatment interval. 5mL of normal saline will be injected at each session. Additionally, patients will receive SHAM treatment over a five-week period, starting at initial placebo injection.

8.1 Schedule of Events:

The events table for the conduct of this study is shown below:

Table 1:

Schedule of Events		Screening	Treatment					Follow Up	
Time Point		0-30 days before randomization	Week 1	Week 2	Week 3	Week 4	Week 5	Month 3	Month 6
Event			Day 0	Day 7 \pm 2	Day 14 \pm 2	Day 21 \pm 2	Day 28 \pm 2	Day 90 \pm 14	Day 180 \pm 14
Informed Consent		X							
Demographics		X							
Medical History		X							
Physical Exam		X							
Doppler Ultrasound		X							X
Questionnaires	IIEF	X						X	X
	EDITS							X	X
	VAS		X	X	X	X	X		
	IPSS	X							X
	SGA								X
Laboratory Tests		X							

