12.1 Adverse Events (AEs)

An adverse event (AE) is defined as any untoward medical occurrence associated with the use of a drug in humans, whether or not considered drug related. An AE can be any unfavorable and unintended sign (including an abnormal laboratory finding), symptom, or disease temporally associated with the study. The event does not need to have a causal relationship with treatment. Common Terminology Criteria for Adverse Events Version 5 (CTCAE) will be used for describing AEs. All urological and/or reproductive system AEs will be recorded. For all other AEs, only events greater than grade 2 will be recorded.

Based on our own pilot data assessing SWT and PRP monotherapy, we have compiled the following data on adverse events (Table 2):

We anticipate there to be few adverse events related to the study. Based on the four published studies and abstracts, including 75 men, only minor adverse events were reported (Bruising 1, Mild Pain 4). No serious adverse events were observed [23-26].

SWT related adverse events	
Transient mild cutaneous purpura	0.10%
Local erythema	0.50%
Local swelling/edema	1.00%
Transient local anesthesia or paranesthesia	1.10%

PPR related adverse events	
Pain greater than 5/10 at time of injection	5.00%
Pain lasting > 5 days	5.00%
Penile bruising	0.00%
Penile fracture	0.00%

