12.2 Serious Adverse Events (SAEs)

A serious adverse event (SAE) is defined as an AE which, in the view of the Investigator results in: 1) Death; 2) a life-threatening event (i.e. an event in which the subject was at risk of death at the time of the event; it does not refer to an event which hypothetically might have caused death if it were more severe); 3) inpatient hospitalization of > 24 hours or prolongation of existing hospitalization; 4) a significant disability/incapacity; or 5) a congenital anomaly/birth defect. Other important medical events may be considered SAEs if, in the opinion of the Investigator, they jeopardize the subject or require intervention to prevent one of the other outcomes listed above. Based on prior investigations, we do not anticipate any SAEs related to the study procedures [23-26].

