12.3 Treatment Emergent Serious Adverse Events (TE-SAEs)

A treatment emergent serious adverse event (TE-SAE) is defined as any serious adverse event for which there is a reasonable possibility that the investigational product caused the adverse event. For the purposes of safety reporting, “a reasonable possibility” means there is evidence to suggest a causal relationship between the study product/procedures and the adverse event.

13. Data and Safety Monitoring Board (DSMB) Charter

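### The primary safety endpoint is labelled treatment emergent but defined as treatment related, so SAEs judged unrelated stay outside the randomised comparison

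*Combined protocol and SAP*

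**What the plan says.** - Section 3.1, primary objective: "To investigate and compare the safety of PRP and SWT vs placebo/sham treatment in men with mild-moderate ED". The synopsis words its primary objective as efficacy, but the endpoint lists in the synopsis and in section 4.1 both put safety first.
- Section 4.1, primary endpoint: "Incidence of treatment emergent serious adverse events (TE-SAEs) in all patients during the study period".
- Section 12.3, definition of the counted event: "any serious adverse event for which there is a reasonable possibility that the investigational product caused the adverse event". The following sentence explains that a reasonable possibility "means there is evidence to suggest a causal relationship between the study product/procedures and the adverse event".
- Section 12.1, on adverse events in general: "The event does not need to have a causal relationship with treatment".
- Section 12.2, on seriousness: "A serious adverse event (SAE) is defined as an AE which, in the view of the Investigator results in" one of a list of outcomes that includes death.
- Section 12.1.2 puts every grade 3 to 5 event into the database and before research committee meetings, related or not. Section 13.4.1.2 has the DSMB review adverse events by masked group.
- Section 14.1 gives Fisher's exact test for categorical data at a significance level of 0.05. It names no SAE analysis.

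**The concern.** Treatment emergent normally describes timing: the event began or worsened after treatment started. Section 12.3 keeps the label but applies a test of cause. The general adverse event definition in 12.1 needs no causal link, and 12.3 brings one back for the single endpoint on which the trial's safety conclusion rests.

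In a randomised trial the control arm exists so that causation can be read from the difference between arms. Judging events one at a time first, and comparing only those that pass, replaces part of that evidence with opinion. An excess made up of events that each look unrelated would not appear in the primary result. Section 12.2 also records that no procedure-related SAEs are expected, and that expectation could itself pull borderline judgements towards unrelated.

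Two gaps add to this. The two sentences of 12.3 disagree on whether the cause must be the product or may be a procedure, which matters most for men given saline and sham. And 12.3 does not say who judges causality or whether that person is blinded.

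**Working it through.** **Text side by side**

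| Question | Section 12.3, first sentence | Section 12.3, second sentence | Sections 3.1 and 4.1 |
|---|---|---|---|
| What must have caused the event? | The product | Product or procedures | Nothing said |
| When must it begin? | Nothing said | Nothing said | Within the study period |
| Can a control-arm SAE count? | Not if read alone | Yes, if linked to a procedure | All patients count, and the arms are compared |
| Does an unrelated SAE count? | No | No | Nothing said |

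The last row is the core of the point, and both sentences of 12.3 give the same answer.

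**The plan's own figure.** Section 14.2 gives 2 × (1.96 + 0.84)² × 0.25 × 0.75 / 0.35² = 2 × 7.84 × 0.1875 / 0.1225 = 24.0 per arm, and 24 / (1 − 0.20) = 30. It reproduces with the inputs as written. It concerns the MCID response rate, a secondary endpoint. No figure is given for the primary endpoint, so only the 30 per arm is carried forward.

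**Precision at 30 per arm** (exact binomial, two-sided 95%)

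- 0/30: upper limit 1 − 0.025^(1/30) = 11.6%.
- 1/30: 3.3%, interval 0.1 to 17.2%.
- 0/60: upper limit 1 − 0.025^(1/60) = 6.0%.

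**Fisher's exact test, 30 against 30.** 1 v 0 gives p = 1.0, 5 v 0 gives p = 0.052 and 6 v 0 gives p = 0.024. With no events in one arm, at least 6 are needed in the other.

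**Effect of the filter.** The documents state neither an all-cause SAE rate nor a share judged related, so both are assumed and taken as equal in the two arms. With rate q and related share r, expected counted events per arm are 30 × q × r, and the chance of none in 60 men is (1 − q × r)^60.

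| Assumed q | r = 25%: expected per arm; chance of none | r = 50% | All SAEs count |
|---|---|---|---|
| 2% | 0.15; 74% | 0.30; 55% | 0.6; 30% |
| 5% | 0.375; 47% | 0.75; 22% | 1.5; 4.6% |
| 10% | 0.75; 22% | 1.5; 4.6% | 3.0; 0.2% |

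Worked cell: q = 5%, r = 25% gives (1 − 0.0125)^60 = 0.47. Under these assumptions, a report of no treatment emergent SAEs would often be produced by the definition rather than by an absence of SAEs.

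**The case against.** The best defence is that little is lost. Grade 3 to 5 events are recorded whatever their cause (12.1.2), the DSMB sees events by masked group and can ask for unmasking (13.4.1.2, 13.5.2), and emergency meetings are possible (13.4). Causation by treatment implies onset after treatment, and 4.1 confines the endpoint to the study period. All of this stands as protection for participants during the trial. None of it puts an unrelated SAE into the primary endpoint or adds an all-cause comparison to 14.1.

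Several stronger readings are tempting, and the documents do not support them:

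- *The control-arm count is zero by definition.* This follows only if the first sentence of 12.3 is read alone. The second admits procedures, 4.1 covers all patients, and control men have blood drawn (9.4), saline injected in the same way as PRP (9.2.1) and sham sessions. The wording is inconsistent, but it does not exclude the control arm.
- *The investigator decides the endpoint while suspecting the allocation.* Section 12.2 gives the investigator the judgement of seriousness. Section 12.3 names nobody for causality. Section 9.4 sets up blinded and unblinded teams, covered syringes and a blood draw in both arms. The fair criticism is that the assessor and the assessor's blinding are unspecified.
- *One judgement changes the primary result.* 1/30 v 0/30 and 0/30 v 0/30 both give p = 1.0, and the intervals overlap heavily.
- *Deaths from other causes go unreported.* Section 7.4(d), "A subject expires during protocol participation from causes other than the study treatment (not due to adverse events", is a list of reasons for leaving the study and not a reporting rule. Death is an SAE under 12.2, and grade 5 events are recorded under 12.1.2. The parenthesis is loose and worth clarifying, no more.
- *Short admissions are lost.* The criterion "inpatient hospitalization of > 24 hours or prolongation of existing hospitalization" concerns seriousness, not causation, and the important-medical-event clause of 12.2 partly covers shorter stays. It is no part of this point.

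**Conclusion.** The definition is wrong as written for a primary endpoint meant to compare randomised arms. Followed literally, section 12.3 removes SAEs judged unrelated before the comparison, leaves the eligibility of control-arm SAEs unclear, and assigns the causality judgement to nobody. This conclusion rests on the text alone.

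The size depends on assumptions. With an all-cause SAE rate of 2 to 5% and a quarter judged related equally in both arms, the chance of a zero count in 60 men rises from 30% to 74% at the lower rate and from 4.6% to 47% at the upper. The effect is on what the primary result means and not on a significance test: at 30 per arm, few plausible SAE counts would reach p < 0.05 under either definition. The claim is not that events are concealed or that control events can never count.

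**What to change.** 1. In 12.3 and 4.1, and in the synopsis to match, define a TE-SAE as any SAE with onset or worsening after the first study treatment (PRP, saline, shockwave or sham) through the Month 6 visit, whatever its judged cause. Count it in both arms.
2. In 14.1, state that the proportion of men with at least one TE-SAE is compared between arms, with exact intervals. Fisher's test is already provided for.
3. Report related SAEs in a supporting table by arm, with one definition of related that covers product and procedures. A blinded member of the existing team records causality before any code break. The order matters because 9.4 allows the investigator to obtain the assignment for important medical reasons.
4. State that 7.4(d) is a withdrawal reason only and that any death remains an SAE under 12.2.

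The cost is mainly wording, since grade 3 to 5 events are already captured. One line should add that every SAE is recorded whatever its grade, because 12.1 limits non-urological events to those above grade 2. The downside is that some background events enter the primary count, in expectation equally in both arms: 30 × 0.02 = 0.6 to 30 × 0.05 = 1.5 per arm at the assumed rates. The change must precede any unblinded analysis, since redefining a primary endpoint afterwards would not be credible.

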13.1 Introduction

This charter defines the roles and responsibilities of the Data and Safety Monitoring Board (DSMB) for the COCKTAIL trial which is funded by the National Institute of Diabetes and Digestive and Kidney Diseases (NIDDK).

The DSMB will serve in accordance with the guidelines set forth in this charter. Typically DSMB members review and agree to the charter at the initial meeting. If changes to the charter are necessary, the DSMB reviews and affirms their agreement with the changes. Their concurrence will be noted in the DSMB meeting summary

13.2 DSMB Responsibilities

Generally, the first responsibility of the DSMB will be to approve the final protocol of the clinical study named above, or the study/studies being undertaken by the research network named above so that the study/studies can begin enrolling patients. After initial approval, and at periodic intervals during the course of the study, the DSMB responsibilities are to:

- Provide input to assist the investigator(s) in protecting the safety of the study participants;
- Provide input to the investigator(s) on major changes to the research protocol, informed consent documents and plans for data and safety monitoring;
- Provide input to the investigator(s) on the progress of the study, including periodic assessments of data quality and timeliness, participant recruitment, accrual and retention, participant risk versus benefit, performance of the study sites, and other factors that may affect study outcomes;
- Review areas of concern regarding the performance of individual sites and provide comment to the investigator(s) on actions to be considered regarding sites that perform unsatisfactorily;

- Consider factors external to the study when relevant information becomes available, such as scientific or therapeutic developments that may have an impact on the safety of the participants or the ethics of the study;
- Provide input to the investigator(s) on modification of the study protocol or possible early termination of the study because of attainment of study objectives, safety concerns, low likelihood of showing a benefit of the intervention, or inadequate performance (such as enrollment and retention problems);
- If appropriate, review the interim analysis of efficacy in accordance with stopping rules which are clearly defined in the protocol and have the concurrence of the DSMB;
- Provide input to the investigator(s) on the desirability of proceeding to the full-scale study at the completion of a feasibility phase, if appropriate;
- Provide input to the investigator(s) on the potential impact of ancillary studies on the integrity of the parent study; and
- Monitor clinical ancillary studies unless an independent monitoring is established

13.3 Membership

The members have been appointed by the investigator(s) and approved by NIDDK. Members of the DSMB shall have no financial, scientific, or other conflict of interest with the study. Collaborators or associates of the investigators in this study are not eligible to serve on the DSMB. Written documentation attesting to absence of conflict of interest is required at least annually, and each time there is a change in site investigators and/or institutions involved in the study.

The investigator(s) will appoint a DSMB chairperson. He or she is responsible for overseeing the meetings and developing the agenda in consultation with the investigator(s).

13.4 DSMB Meetings

The DSMB will typically meet twice a year, or as deemed necessary. A quorum of more than half of the DSMB members is required in order to convene a meeting of the DSMB.

Meetings shall be closed to the public because discussions may address confidential patient data. Meetings are attended, when appropriate, by the principal investigator and members of his/her staff, as well as the study statistician. Meetings may be convened as conference calls or webinars, as well as in person. In special circumstances, the meetings may also be conducted by email. An emergency meeting of the DSMB may be called at any time by the DSMB chairperson should questions of patient safety arise.

13.4.1 Meeting Format

An appropriate format for DSMB meetings consists of an open, closed (if the DSMB is monitoring a study in which the investigators are masked in any way), and executive session. This format may be modified as needed.

13.4.1.1 Open Session

Members of the DSMB, the principal investigator and members of the steering committee, including the study biostatistician may attend the open session. Issues discussed will include the conduct and progress of the study, including patient recruitment, data quality, general adherence and toxicity issues, compliance with protocol, and any other logistical matters that may affect either the conduct or outcome of the study. Proposed protocol amendments will also be presented in this session. Patient-specific data and treatment group data may not be presented in the open session.

13.4.1.2 Closed Session

The closed session will be attended only by DSMB members, and the unmasked study biostatistician. The discussion at the closed session is completely confidential. All materials from the closed session will be destroyed at the end of the meeting.

Analyses of outcome data are reviewed by masked intervention groups, including baseline characteristics, primary and secondary outcomes, adverse events, adherence and dropouts, and examination of any relevant subgroups. The DSMB may request unmasking of the data for either safety or efficacy concerns. Procedures to accomplish unmasking of either individual or treatment group data are to be specified in the Data and Safety Monitoring Plan.

13.4.1.3 Executive Session

The executive session will be attended by DSMB members only, who will discuss the information presented during the closed and open sessions and provide input on the continuation or termination of the study, protocol modification or other changes to the conduct of the study. The DSMB can be unmasked at any time if trends develop either for benefit or harm to the participants.

The DSMB will make a recommendation for either continuation or termination of the study. Termination may be suggested by the DSMB at any time. Reasons for early termination include:

- Serious adverse effects in entire intervention group or in a dominating subgroup;
- Greater than expected beneficial effects;
- A statistically significant difference by the end of the study is improbable;
- Logistical or data quality problems so severe that correction is not feasible.

Sound rationale for either decision (continuation or termination of the study) should be presented.

13.5 Reports to the DSMB

Reports will be prepared by the unmasked biostatistician on a quarterly or semi-annual basis as decided by the investigator(s) and the DSMB. The reports will be distributed to the DSMB at least 10 days prior to a scheduled meeting. These reports shall be provided in sealed envelopes within an express mailing package, by secure email, or by access to a secure website, as the DSMB prefers.

Data reports for randomized clinical studies or any study in which the investigators are masked generally consist of two parts: an Open Report and a Closed Report.

